Appendix 4. RAND-36 Questionnaire

Participant's Initials _____ Date _____

The following items are about activities you might do during a typical day. Does your health now limit you in these activities? If so, how much?

(Circle One Number on Each Line)

	Yes, Limited a Lot	Yes, Limited a Little	No, Not limited at All
3. Vigorous activities, such as running, lifting heavy objects, participating in strenuous sports	[1]	[2]	[3]
4. Moderate activities, such as moving a table, pushing a vacuum cleaner, bowling, or playing golf	[1]	[2]	[3]
5. Lifting or carrying groceries	[1]	[2]	[3]
6. Climbing several flights of stairs	[1]	[2]	[3]
7. Climbing one flight of stairs	[1]	[2]	[3]
8. Bending, kneeling, or stooping	[1]	[2]	[3]
9. Walking more than a mile	[1]	[2]	[3]
10. Walking several blocks	[1]	[2]	[3]
11. Walking one block	[1]	[2]	[3]
12. Bathing or dressing yourself	[1]	ş — —	[3]

Participant's Initials--- Date _____

During the **past 4 weeks**, have you had any of the following problems with your work or other regular daily activities **as a result of your physical health?**

(Circle One Number on Each Line)

	Yes	No
13. Cut down the amount of time you spent on work or other activities	1	2
14. Accomplished less than you would like	1	2
15. Were limited in the kind of work or other activities	1	2
16. Had difficulty performing the work or other activities (for example, it took extra effort)	1	2

During the **past 4 weeks**, have you had any of the following problems with your work or other regular daily activities **as a result of any emotional problems** (such as feeling depressed or anxious)?

(Circle One Number on Each Line)

	Yes	No	
17. Cut down the amount of time you spent on work or other activities	1	2	
18. Accomplished less than you would like	1	2	
19. Didn't do work or other activities as carefully as usual	1	2	A second second as a second se

Confldenfia!

Participant's Initials _____ Date ____

20. During the **past 4 weeks**, to what extent has your physical health or emotional problems interfered with your normal social activities with family, friends, neighbors, or groups?

(Circle One Number)

Not at all 1

Slightly 2

Moderately 3

Quite a bit 4

Extremely 5

21. How much bodily pain have you had during the past 4 weeks?

(Circle One Number)

None 1

Very mild 2

Mild 3

Moderate 4

Severe 5

Very severe 6

22. During the **past 4 weeks**, how much did **pain** interfere with your normal work (including both work outside the home and housework)?

(Circle One Number)

Not at all 1

A little bit 2

Moderately 3

Quite a bit 4

Extremely 5

These questions are about how you feel and how things have been with you **during the past 4 weeks.** For each question, please give the one answer that comes closest to the way you have been feeling.

How much of the time during the past 4 weeks

Participant's Initials

Date

(Circle One Number on Each Line)

	All of the Time	Most of the Time	A Good Bit of the Time	Some of the Time	A Little of the Time	None of the Time
23. Did you feel full of pep?	1	2	3	4	5	6
24. Have you been a very nervous person?	1	2	3	4	5	6
25. Have you felt so down in the dumps that nothing could cheer you up?	1	2	3	4	5	6
26. Have you felt calm and peaceful?				4	5	6
27. Did you have a lot of energy?				4	5	6
28. Have you felt downhearted and blue?				4	5	6
29. Did you feel worn out?				4	5	6
30. Have you been a happy person?				4	5	6
31. Did you feel tired?	1	2	3	4	5	6

Participant's Initials _____ Dale _____

32. During the **past 4 weeks**, how much of the time has your **physical health or emotional problems** interfered with your social activities (like visiting with friends, relatives, etc.)?

(Circle One Number)

All of the time 1

Most of the time 2

Some of the time 3

A little of the time 4

None of the time 5

How TRUE or FALSE is each of the following statements for you.

(Circle One Number on Each Line)

	Definitely True	Mostly True	Don't Know	Mostly False	Definitely False
33. ∎seem to get sick a little easier than other people	1	2	3	4	5
34. ∎am as healthy as anybody ∎ know	1	2	3	4	5
35. ∎expect my health to get worse	1	2	3	4	5
36. My health is excellent	1	2	3	4	5

Adapted fi om: Ware JE Jrl, Sherbourne CD. The MOS 36-item short-form health survey (SF-36).!. Conceptual framework and item selection. *Med Care*. 1992; 30:473-83.

Jason Pharmaceuticals) Inc. BI0-1607 (MED 019) 21 June 2016; Version 1.7 **Cm?fidential**

Appendix 5. l'rogram Questionnaire

Visit 2	Visit 4	Visit 5	Visit 6	Visit 7
-	domization no			
Participant's	Initials	Date		

Ouestions 1 and 2 for All Groups at Visit 2 only:

- I. Describe your physical activity at work or school, on average, over the last 4 weeks?
 - **O** Very Light (sitting at your computer or desk most of the day)
 - O Light (light industrial work, sales or office work that comprises light activity)
 - **O** Moderate (cleaning, kitchen stan:or delivering mail on foot or by bicycle)
 - **O** Heavy (heavy industrial work, construction work or farming)
- 2. Describe your physical activity at leisure time, on average, over the last 4 weeks?
 - **O** Very Light (almost no activity at all)
 - O Light (walking, non-strenuous cycling or gardening approximately once a week)
 - **O** Moderate (regular activity at least once a week, e.g., walking, bicycling (including to work) or gardening)
 - **O** Active (regular activities more than once a week, e.g., intense walking, bicycling or sports)
 - **O** Very Active (strenuous activities several times a week)

Ouestions 3, 4, and 5 for All Groups to be answered at Visits 4, 5, 6, and 7:

DIRECTIONS: Please draw a single, vertical_straight, mark along the line to indicate your response. The vetiiealline must intersect with the horizontal line. Please do not circle any words. Your response should indicate how you are feeling at this moment.

3.

Over the last 4 weeks, how well did you follow your assigned weight loss plan?

Not at all

Perfectly

VAS measurement (mm):

- 4. Describe your physical activity at work or school, on average, over the last 4 weeks?
 - **O** Very Light (sitting at your computer or desk most of the day)
 - **O** Light (light industrial work, sales or office work that comprises light activity)
 - O Moderate (cleaning, kitchen staff, or delivering mail on foot or by bicycle)
 - **O** Heavy (heavy industrial work, construction work or farming)
- 5. Describe your physical activity at leisure time, on average, over the last 4 weeks?
 - **O** Very Light (almost no activity at all)
 - **O** Light (walking, non-strenuous cycling or gardening approximately once a week)
 - **O** Moderate (regular activity at least once a week, e.g., walking, bicycling (including to work) or gardening)
 - **O** Active (regular activities more than once a week, e.g., intense walking, bicycling or sports)
 - **O** Very Active (strenuous activities several times a week)

Ouestion 6: MEDD and TSFL groups only to be answered at Visits 4, 5, 6, and 7:

6. Over the last 4 weeks, how many Medifast meal replacement products did you consume on **MOST DAYS?** (Do not count Flavors of Home meals or Medifast Snacks in your count.)

Please circle response (limit to one answer).

- 0
- •
- 2
- 3
- 4
- 5
- 6
- >6

Appendix 6. Satisfaction and Health/Well-being Questionnaire*

Based on your experience throughout the study with the weight loss plan you were assigned, how much would you agree/disagree with the following statements?

	1 = Strongly Disagree	2 = Disagree	3 = Neither Agree or Disagree	4 = Agree	5 = Strongly Agree
I. I would recommend this weight loss plan.	Ο	Ο	Ο	Ο	Ο
? The weight loss n was easy to low.	Ο	ο	Ο	Ο	O
3. I feel my sleep has improved.	0	Ο	Ο	Ο	Ο
4. The weight loss plan was convenient.	O	O	0	O	О
5. The weight loss plan fit my lifestyle.	Ο	0	0	Ο	Ο
6. I feel my overall health has improved.	0	0	Ο	Ο	Ο
7. My clothes fit better.	Ο	Ο	0	О	0

	1 = Strongly Disagree	2 = Disagree	3 = Neither Agree or Disagree	4 = Agree	5 = Strongly Agree
8. I have more energy	Ο	Ο	0	0	0
9. I believe the support provided was the key to my success on the weight loss plan.	0	0	O	Ο	Ο
10. I felt my hunger was under control on the weight loss plan.	Ο	Ο	Ο	0	0
11. I feel I achieved real success.	Ο	Ο	Ο	Ο	Ο
12. I believe my experience with this weight loss plan will help me to sustain a healthy lifestyle.	0	0	0	0	
The weight loss plan was effective for me.	Ο	Ο	ο	0	Ο
14. I feel better about myself.	Ο	0	0	Ο	Ο
15. I feel the weight loss plan was a healthy way to lose weight.	Ο	O	Ο	Ο	Ο

	1 = Strongly Disagree	2 = Disagree	3 = Neither Agree or Disagree	4 = Agree	5 = Strongly Agree
16. I feel more confident	0	0	0	0	0
17. I learned habits for a healthier lifestyle.	Ο	0	Ο	Ο	Ο
18. The program tools were easy to use.	0	0	0	Ο	Ο
19. I feel better physically.	Ο	0	Ο	0	O
20. I feel my overall wellbeing has improved.	0	0	0	0	0

*The order of the above questions will be randomly presented to the participants.

## ABBREVIATIONS

AE	adverse event
ALP	alkaline phosphatase
ALT	alanine aminotransferase
ANCOVA	analysis of covariance
ANOVA	analysis of variance
AST	aspartate aminotransferase
BMI	body mass index
BUN	blood urea nitrogen
CO2	carbon dioxide
DXA	dual energy x-ray absorptiometry
eCRF	electronic case report form
FDA	Food and Drug Administration
HIPAA	Health Insurance Portability and Accountability Act
hs-CRP	high-sensitivity C-reactive protein
ICH	International Conference on Harmonization
IQR	Inter-Quartile Range
IRB	Institutional Review Board
ITT	intent to treat
IWQOL	Impact of Weight on Quality of Life
kg	kilogram
LOCF	Last Observation Carried Forward
MEDD	Medifast Direct
m	meter
m^2	meter squared
mg	milligram
mITT	Modified intent to treat
mL	milliliter
mm Hg	millimeters of mercury
PAL	physical activity level
QoL	quality of life
SEM	standard error of the mean
SOP	standard operating procedure
TSFL	Take Shape For Life
tel	telephone
VAS	visual analog scale

## 1.0. STUDY OBJECTIVES

The objective of this study is to evaluate the effects of two commercially available weight loss programs, TSFL and MEDD, each compared to a self-directed control diet, on changes in body weight in apparently healthy overweight and obese men and women.

## 2.0. TRIAL DESIGN AND VISIT STRUCTURE

This randomized, controlled, 16-week parallel study includes one screening visit (Visit 1; week -1), one baseline visit (Visit 2; week 0), and five clinic visits (Visits 3,4,5,6, and 7; weeks 2, 4, 8, 12, and 16). Subjects will be randomly assigned in 1:1:1 ratio to one of the three groups (TSFL Program Group, MEDD Program Group, or Control Group) within which the subjects will receive the following interventions:

- **TSFL Program Group:** The TSFL Program group will be assigned to the Optimal Weight 5 & 1 Plan™ for weight loss. This is a portion-controlled, nutritionally balanced, low calorie weight loss meal plan (800-1000 kcal/day) that consists of five Medifast meal replacements, one lean and green meal, and one optional snack each day. The Medifast meal replacements are nutrient dense and fortified with 24 vitamins and minerals to ensure adequate micronutrient nutrition while on a calorie restricted meal plan. All Medifast meal replacements share a similar nutritional profile, allowing them to be used interchangeably. All Medifast meal replacements required for the meal plan will be provided to the TSFL Group participants throughout the 16-week weight loss period of the study. The lean and green meal is a self-prepared meal consisting of a specified amount of lean protein, non-starchy vegetables, and healthy fats. Participants will purchase and prepare foods used for the lean and green meals on their own. Additionally, the Medifast Flavors of Home® products offer a “heat and serve” alternative to the self-prepared lean and green meal for occasional use. TSFL participants will receive up to six Flavors of Home products per month during the study. TSFL participants will receive a list of self-selected foods (purchased by the participants) that can be used for the optional snack. In addition, participants will also be provided with up to two boxes (i.e., 14 individual packets) of Medifast snacks which can serve as a portable, pre-portioned, ready-to-eat alternate snack option.

This TSFL group will have regularly scheduled coaching sessions starting at Visit 2 (week 0) with an assigned research assistant trained to function as a TSFL coach (hereinafter referred to as the TSFL Coach) for the duration of the study. The TSFL coach training will take place before the study and will utilize a training protocol mimetic of current training received by new TSFL Coaches. The coaching schedules and content will meet the TSFL coaching standards of practice. Coaching, for the purpose of this study, will take place via telephone. The initial coaching session (45 min in length) will occur the day of Visit 2 (week 0) as participants will be instructed to start their weight loss program on the day following the randomization visit (day 1). If the coaching session does not take place, participants will be instructed to start their weight loss program on day 1 regardless (a protocol deviation form must be submitted). Participants will have access to TSFL written support tools and monthly e-mailed newsletters throughout the study to assist with weight loss. Participants will also have limited

telephone and e-mail access during the study to the Medifast Nutrition Support Team (available when a question exceeds the scope of the TSFL Coach training), which is consistent with the commercially available program.

- **MEDD Program Group:** Participants randomized to the MEDD group will be assigned to the Medifast Achieve™ Plan (4 & 2 & 1 Plan®) for weight loss. The Achieve Plan is a portion-controlled, nutritionally balanced, reduced energy (1100-1300 kcal/day) meal plan that consists of four Medifast meal replacements, two lean and green meals, and one healthy snack. The Medifast meal replacements and the lean and green meals are the same as those described above for the TSFL Group. Briefly, Medifast meal replacements are portion-controlled, nutrient dense, and fortified with 24 vitamins and minerals. All Medifast meal replacements share a similar nutritional profile, allowing them to be used interchangeably. Medifast meal replacements required for the program will be provided to the MEDD Group participants throughout the study. The lean and green meal is a self-prepared meal consisting of a specified amount of lean protein, non-starchy vegetables, and healthy fats. Participants will purchase and prepare foods used for the lean and green meals on their own. Additionally, the Medifast Flavors of Home® products offer a “heat and serve” alternative to the self-prepared lean and green meal for occasional use. MEDD participants will receive up to twelve Flavors of Home products per month during the study. The healthy snack will consist of a self-selected serving of fruit, dairy, or grain purchased by the participant, or one of Medifast’s portable, pre-portioned, ready-to-eat Medifast snacks can be used as a healthy snack. Participants will receive up to two boxes (i.e., 14 individual packets) of Medifast snacks per month.

Participants will be dispensed study-specific printed materials (including the “Getting Started Instructions”) at Visit 2 (week 0) and will have one telephone call with a Medifast Nutrition Support Team member prior to 17:00 h EST at Visit 2 (week 0) to receive instruction on the meal plan and support materials as participants will be instructed to start their weight loss program on the day following the randomization visit (day 1). If the telephone call does not take place, participants will be instructed to start their weight loss program on day 1 regardless (a protocol deviation form must be submitted). Participants will also have telephone and e-mail access to the Medifast Nutrition Support Team and Medifast online tools throughout the study. Participants in the MEDD group will be encouraged to track weight and food intake and access MEDD written, online, and virtual support tools to use at their discretion.

- **Control:** The Control group will follow a self-directed diet, which is a food-based, reduced-calorie diet, consistent with the 2015 Dietary Guidelines for Americans (See Supplementary Materials). This group will receive a one-on-one personal instruction session (10-15 min) with a trained member of the study staff at the Visit 2 (week 0) clinic visit. During this session, daily energy intake targets will be determined for each participant using the National Institutes of Health body weight planner ([www.niddk.nih.gov/health-information/health-topics/weight-control/body-weight-planner/Pages/bwp.aspx](http://www.niddk.nih.gov/health-information/health-topics/weight-control/body-weight-planner/Pages/bwp.aspx)). The personalized daily energy intake level will be specific to each participant’s 16-week weight loss goal, targeting 7% weight loss over the 16-week weight loss period, consistent with recent obesity treatment guidelines (Jensen 2014). Participants will receive publicly available information from the USDA Choose MyPlate

program, including a handout with a meal plan from the website to match their target energy intake, as well as instruction to utilize the [www.choosemyplate.gov](http://www.choosemyplate.gov) website. Participants with target energy intakes of <1600 kcal per day will be instructed to take a multi-vitamin of their choosing (not marketed to enhance or benefit weight loss, energy, metabolism, etc.) to ensure adequate intake of micronutrients. Participants will be instructed to start their weight loss program on the day following randomization (day 1). In keeping with the self-directed nature of this control group, participants will not receive further instructions or personal support during the weight loss period.

### **3.0. SIZE OF TRIAL POPULATION**

A standard deviation of 15.0 lb for change in body weight over 16 weeks was derived from the largest variability observed in a previous study by Davis et al. (2010) that compared weight loss over 16 weeks on the Medifast 5 & 1 Plan® (-29.8 ± 13.0 lb) vs. a food-based isocaloric control diet (-14.3 ± 15.0 lb). Using this estimate of expected variability and accounting for a more conservative mean difference in weight loss between groups over a similar timeframe, an evaluable sample of 55 participants in each group (165 total) will provide 80% power to detect a difference of 9.0 pounds (an effect size  $d$  of 0.60). This assumes a nominal  $\alpha = 0.025$  (two-sided) accounting for two primary comparisons, each Medifast group compared to the control group, in order to maintain an overall type I error of  $\alpha = 0.05$ . To account for possible attrition, a total sample of 198 participants will be randomized.

Subjects will be randomized to one of three groups (1:1:1 ratio) stratified by sex to ensure each group is allocated a maximum of 25% male participants. Additionally, the total study sample will be limited to  $\leq 10\%$  of participants with a BMI between  $\geq 27.0$  and  $< 30.0$  kg/m^2, but randomization will not be stratified by BMI.

### **4.0. PERSONNEL RESPONSIBLE FOR DATA ANALYSIS**

Data analyses will be carried out by personnel from Biofortis.

### **5.0. ANALYSIS POPULATIONS**

All statistical analyses will be conducted using SAS® software for Windows (version 9.4 or higher, Cary, NC).

An Intent-To-Treat (ITT) population will include all subjects who were randomized into the study. A modified ITT (mITT) population will include all randomized participants that had at least one post-baseline weight measurement. In addition, a Completers population will comprise subjects who were randomized into the study and completed all clinic visits during the entire 16-week study period.

All decisions regarding population assignment will be documented prior to database lock.

### **6.0. PRESENTATION OF SUBJECT DISPOSITION**

Frequency counts and percentages for all subjects who are screened, randomized, complete the study, and discontinue early will be presented. Information will be presented for subjects who withdraw early on the visits at which withdrawal occurred and the intervention condition(s) completed. In addition, frequency counts and percentages of subjects' reported reasons for discontinuation will be summarized.

## 7.0. PRESENTATION OF SCREENING/BASELINE VARIABLES

Variables collected at screening (Visit 1) will be summarized and presented. In addition, vital signs measurements collected from Visits 1 to 7 will also be summarized and presented. Descriptive statistics (number of subjects, mean, standard error of the mean (SEM), median, inter-quartile limits, minimum, and maximum values) will be presented for the continuous variables. Frequency counts and percentages will be presented for the categorical variables. The following variables will be presented:

- Demographic characteristics: (*Visit 1*)
  - Gender (male, female)
  - Age (years)
  - Race (White, Black/African American, American Indian or Alaskan Native, Asian or Pacific Islander, Multiracial Origin, or Other)
  - Ethnicity (Hispanic/Latino or Not Hispanic/Latino)
  - Weight (kg)
  - Height (cm)
  - BMI ( $\text{kg}/\text{m}^2$ ) as continuous and categorical variables (frequency counts and percentages of subjects randomized to each BMI strata for each group)
  - Smoking status
  - Education
  - Fasting glucose (mg/dL)
  
- Vital signs measurements: (*Visits 1 to 7*)
  - Systolic blood pressure (mmHg)
  - Diastolic blood pressure (mmHg)
  - Heart rate (bpm)

The chemistry and hematology profiles for each subject at screening visit (Visit 1) will be reviewed by the clinical investigators (MD) and any findings of clinical significance will be documented. No descriptive statistics will be generated.

## 8.0. OUTCOME ANALYSIS

### 8.1. Primary Outcome Variable

The primary outcome variable will be change (absolute and percent change) in body weight from baseline (Visit 2; week 0) to end of study (Visit 7; week 16)

### 8.2. Secondary Outcome Variables

Secondary outcome variables include values of the following variables at post-randomization visits as stated:

- Change (absolute and percent change) in body weight from baseline (Visit 2; week 0) to Visits 3, 4, 5, and 6 (weeks 2, 4, 8, and 12)
- Proportion of participants achieving  $\geq 5\%$  and  $\geq 10\%$  loss of baseline body weight at each post-randomization visit Visits 3, 4, 5, 6, and 7 (weeks 2, 4, 8, 12, and 16)

- Change (absolute and percent change) in the following body composition parameters (measured via DXA) from baseline (Visit 2; week 0) to Visits 4, 5, 6, and 7 (weeks 4, 8, 12, and 16)
  - Total fat mass (kg)
  - Total lean mass (non-bone fat free mass) (kg)
  - Percent body fat (expressed as percentage of total body mass)
  - Android fat and lean mass (g)
  - Gynoid fat and lean mass (g)
  - Abdominal visceral fat mass (g) and volume (cm^3)
- Absolute change in body circumference parameters from baseline (Visit 2; week 0) to Visits 4, 5, 6, and 7 (weeks 4, 8, 12, and 16)
  - Waist circumference (cm)
  - Hip circumference (cm)
  - Chest circumference (cm)
  - Dominant upper arm circumference (cm)
  - Dominant thigh circumference (cm)
  - Total body circumference (sum of all five measures) (cm)
  - Waist to hip ratio
- Absolute change in QoL questionnaire outcomes (domain and/or total scores) from baseline (Visit 2; week 0) to Visits 5 and 7 (weeks 8 and 16). QoL will be measured using both RAND-36 Questionnaire (uses same questions as the Short Form (36) Health Survey Questionnaire (Ware JE, et al. 1992)) and IWQOL-Lite Questionnaire.
  - RAND 36-item Health Survey Questionnaire assesses the eight health scales: physical functioning (10 questions), role limitations due to physical health problems (4 questions), role limitations due to emotional problems (3 questions), energy/fatigue (4 questions), emotional well-being (5 questions), social functioning (2 questions), pain (2 questions), and general health (5 questions). The scales' scores will be calculated as described on the RAND website ([http://www.rand.org/health/surveys\\_tools/mos/36-item-short-form/scoring.html](http://www.rand.org/health/surveys_tools/mos/36-item-short-form/scoring.html)).
  - IWQOL-Lite Questionnaire (Kolotkin RL, et al. 2001) is a 31-question self report instrument to assess obesity specific quality of life and consists of five domains: Physical Function (11 questions), Self-Esteem (7 questions), Sexual Life (4 questions), Public Distress (5 questions), and Work (4 questions). The domain scores will be the sum of the ratings on questions that correspond to the specific domain. A total score (all 31 questions) will also be presented.
- Participant satisfaction and health/well-being assessed using the Satisfaction and Health/Well-Being Questionnaire at Visit 7 (week 16). Responses will be coded as follows: “1” and “2” = “Disagree”, “3”= “Neither agree nor disagree”, and “4” and “5”= Agree.
- Absolute change in hs-CRP from baseline (Visit 2; week 0) to Visit 7 (week 16)
- Weight loss program adherence assessed at Visits 4, 5, 6, and 7 (weeks 4, 8, 12, and 16) based on the Program Questionnaire. Adherence will be calculated based on self-reported TSFL/MEDD meal replacement product consumption (active groups only) and a single question VAS rating adherence to their assigned weight loss program (all groups). For the self-reported TSFL/MEDD meal replacement product consumption, if the subject encircled “>6”, it will be coded as “7”. Also, questions (1,2) and (4,5) of the Program Questionnaire will be scored as:

		Leisure Time Activity				
		Very Light	Light	Moderate	Active	Very Active
Working/School Activity	Very Light	1.4	1.5	1.6	1.7	1.9
	Light	1.5	1.6	1.7	1.8	2.0
	Moderate	1.6	1.7	1.8	1.9	2.2
	Heavy	1.7	1.8	1.9	2.1	2.3

- Participation at assigned coaching sessions as a measure of adherence for the TSFL group.
- Utilization of Nutrition Support for the TSFL and MEDD group.

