Counts and percentages for questionnaire responses will be presented by intervention group for ordinal outcomes (e.g. Likert scales). Differences between control and each active group will be assessed using a generalized linear model with a cumulative logit link and multinomial distribution specified. Initial repeated measures models will contain terms for intervention, week, intervention by week interaction, and sex. Models will be reduced using a backward selection method until only significant terms or intervention remains in the model. Pairwise comparisons between control and each active group at each post-randomization visit will be conducted using Dunnett's correction for multiple comparisons between each Medifast group vs. control.

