### 9.0. STATISTICAL METHODS

Descriptive statistics (number of subjects, mean, SEM, median, interquartile limits, minimum and maximum) will be presented for quantitative variables. Ratings for categorical variables will be presented as counts and percentages. All tests of significance, unless otherwise stated, will be performed at alpha=0.05, two-sided.

Baseline comparisons for demographic characteristics between control and intervention groups will be completed with the Chi-square test, Fisher’s exact (two-tail) test, or analysis of variance (ANOVA), as appropriate.

Analysis of covariance (ANCOVA) will be used to assess differences among intervention groups in the primary and continuous secondary outcome variables at each post-randomization visit. The ANCOVA model will contain a term for intervention, with sex and baseline measures as covariates. Least squares mean values and corresponding SEM will be derived from the final ANCOVA model for each intervention group.

Counts and percentages of subjects who experience weight loss of  $\geq 5\%$  and  $\geq 10\%$  between baseline (Visit 2) and each post-randomization visit (visits 3, 4, 5, 6, and 7) will be presented. Differences among intervention groups in subjects with weight loss of  $\geq 5\%$  and  $\geq 10\%$  will be assessed using a generalized linear model with a logit link and binomial distribution specified. The model will contain a term for intervention, with sex as a covariate.

Differences among intervention groups in individual Satisfaction and Health/Well-being questionnaire scores will be assessed using a generalized linear model with a cumulative logit link and multinomial distribution specified. The model will contain a term for intervention, with sex and absolute change in weight as covariates.

For the analyses of body weight, body composition parameters, and body circumference parameters, each active group will be compared to the control group using a step-down Dunnett adjustment for multiple comparisons when a significant treatment effect is observed. Meanwhile,

no adjustments will be done on control vs. active comparisons on the remaining outcome variables.

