		Min, Max	Min, Max	Min, Max	Min, Max	
	Change Week 16	N	N	N	N	
		Mean (SEM)	Mean (SEM)	Mean (SEM)	Mean (SEM)	
		Median	Median	Median	Median	
		Q1, Q3	Q1, Q3	Q1, Q3	Q1, Q3	
		Min, Max	Min, Max	Min, Max	Min, Max	
	Within group p-value+	x.xxx(r)	x.xxx(r)	x.xxx(r)		

Table 4.7  
 Secondary Outcome Variable: RAND Questionnaire Outcomes (Visits 5 and 7) Descriptive Statistics and P-values

Parameter	Week	Control	TSFL	MEDD	Intervention p-value ^
		LS Mean (SEM)	LS Mean (SEM)	LS Mean (SEM)	x.xxx(r)
		Group comparison p-value*		x.xxx(r)	x.xxx(r)

^ p-values are from ANCOVA models, adjusted for sex and baseline values at Visit 2.

(r) indicates rank transformation was employed.

\* p-values are NOT adjusted for multiple comparisons (each active group vs. control group)

+ p-values are generated from paired t-test or sign-rank test, as appropriate

**NOTE: This table will be presented for the eight scale scores of the RAND questionnaire (Physical functioning, Role limitations due to physical health, Role limitations due to emotional Problems, Energy/fatigue, Emotional well-being, Social functioning, Pain, General health).**

Table 4.8.1  
 Secondary Outcome Variable: Satisfaction and Health/Well-being Questionnaire Descriptive Statistics

Parameter	Week	Rating	Control	TSFL	MEDD
Recommend Weight Loss Plan	Week 16 (Visit 7)	Strongly Disagree	N (%)	N (%)	N (%)
		Disagree	N (%)	N (%)	N (%)
		Neither Agree or Disagree	N (%)	N (%)	N (%)
		Agree	N (%)	N (%)	N (%)
		Strongly Agree	N (%)	N (%)	N (%)

NOTE: This table will be presented for ratings for each question of the Satisfaction and Health/Well-being questionnaire.

Table 4.8.2  
 Secondary Outcome Variable: Satisfaction and Health/Well-being Questionnaire (Recoded) Descriptive Statistics and P-values

Parameter	Week	Rating	Control	TSFL	MEDD	Intervention p-value
Recommend Weight Loss Plan	Week 16 (Visit 7)	Disagree	N (%)	N (%)	N (%)	x.xxx
		Neither Agree or Disagree	N (%)	N (%)	N (%)	
		Agree	N (%)	N (%)	N (%)	
		Group comparison p-value*		x.xxx	x.xxx	

\* p-values are NOT adjusted for multiple comparisons

NOTE: This table will be presented for ratings for each question of the Satisfaction and Health/Well-being questionnaire.

Table 4.9  
Secondary Outcome Variable: Program Questionnaire (Visits 4, 5, 6, 7) Descriptive Statistics

Parameter	Week		Control	TSFL	MEDD
Physical Activity Level	Baseline ( Week 0)	N	N	N	N
	(Visit 2)	Mean (SEM)	Mean (SEM)	Mean (SEM)	Mean (SEM)

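### The SAP collapses the five-level satisfaction and well-being ratings to three and tests only the collapsed version, which costs these secondary comparisons precision by an amount the documents do not fix

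*SAP*

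**What the plan says.** - **The instrument.** Protocol Appendix 6 has 20 items, each on five ordered levels starting at "1 = Strongly Disagree" and ending at strong agreement. It is completed once, at week 16.
- **The protocol's analysis.** Protocol 8.2.2 states: "Counts and percentages for questionnaire responses will be presented by intervention group for ordinal outcomes (e.g. Likert scales". It then assigns such outcomes a cumulative logit model for each active group against control. It mentions no merging of levels.
- **The SAP's coding.** SAP 8.2 introduces the recode with "Responses will be coded as follows". Ratings 1 and 2 become disagree, 3 stays neutral, and 4 and 5 become agree.
- **The SAP's model.** SAP 9.0 specifies a "generalized linear model with a cumulative logit link and multinomial distribution specified" for the individual questionnaire scores, adjusted for sex and absolute weight change. It does not say which coding the model uses.
- **The shells settle it.** Table 4.8.1, "Secondary Outcome Variable: Satisfaction and Health/Well-being Questionnaire Descriptive Statistics", has five levels with counts and percentages only. Table 4.8.2, "Satisfaction and Health/Well-being Questionnaire (Recoded) Descriptive Statistics and P-values", has three levels and carries both the intervention p-value and the group-comparison p-values.
- **Error rate.** "All tests of significance, unless otherwise stated, will be performed at alpha=0.05, two-sided"; for these items "no adjustments will be done on control vs. active comparisons on the remaining outcome variables".
- **Changes from the protocol.** SAP Section 14 lists five changes. The recode is not among them.

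**The concern.** A cumulative logit model is made for ordered categories. Going from three levels to five adds two intercepts and leaves the treatment parameter as it is. A sparse level does not by itself prevent the fit. Merging levels first removes the distinction between agreeing and strongly agreeing, and between disagreeing and strongly disagreeing, from every test.

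At stake is the chance of detecting a difference between each program and control on a listed secondary outcome, using data that are collected and tabulated anyway. The trial was sized on weight change alone, so these items have no planned power in reserve.

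**Working it through.** **The plan's own figure.** The documents give no power, effect size or response distribution for these items. The only sample-size figure is for weight: 55 evaluable per group, difference 9.0 lb, SD 15.0 lb, two-sided alpha 0.025. The noncentral t gives 80.7% power at 55 and 79.9% at 54, so 55 is reproduced. It is borrowed below as an illustrative arm size.

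**Formula.** For two equal arms under proportional odds, near the null and without covariates, information on the log odds ratio is proportional to 1 - Σp³, where p are the category proportions. Merging categories with proportions a and b lowers this by (a+b)³ - a³ - b³ = 3ab(a+b). That is positive whenever both are occupied, so some information is always lost. The loss is 1 - (three-level value)/(five-level value).

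**One case in full.** Assume .05/.10/.20/.40/.25 for levels 1 to 5.
- Five levels: 1 - (.000125 + .001 + .008 + .064 + .015625) = .911.
- Three levels (.15/.20/.65): 1 - (.003375 + .008 + .274625) = .714.
- Loss: 1 - .714/.911 = 22%. Of the drop of .197, the agree merge accounts for 3 × .40 × .25 × .65 = .195.

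**Range.** Every distribution here is assumed. The power column uses 55 per arm, two-sided alpha 0.05, the listed distribution in the control arm, an odds ratio of 3 toward agreement, and exact Fisher information for the cumulative logit model without covariates. A dash means not computed.

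| Assumed responses, levels 1-5 | 1-Σp³, five | 1-Σp³, three | Loss near null | Power at OR 3, five vs three |
|---|---|---|---|---|
| .10/.20/.40/.20/.10 | .918 | .882 | 4% | 87% vs 84% |
| .10/.20/.30/.30/.10 | .936 | .882 | 6% | 87% vs 83% |
| .20 each | .960 | .864 | 10% | 88% vs 82% |
| .05/.15/.25/.35/.20 | .930 | .810 | 13% | 86% vs 75% |
| .05/.10/.20/.40/.25 | .911 | .714 | 22% | 85% vs 65% |
| .05/.10/.15/.40/.30 | .904 | .650 | 28% | - |
| .03/.07/.15/.45/.30 | .878 | .574 | 35% | 84% vs 52% |
| .02/.05/.08/.40/.45 | .844 | .385 | 54% | 80% vs 35% |
| .02/.03/.05/.35/.55 | .791 | .271 | 66% | - |

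Away from the null, the loss grows when the active arm moves further toward agree. For .05/.10/.20/.40/.25 it is 32% at OR 2 (power 50% vs 36%) and 39% at OR 3.

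The split within the agree end matters as well as its size. With .03/.07/.20/.60/.10 the loss is 16%, and with .02/.03/.05/.10/.80 it is 44%. The bands are guides, not bounds.

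**The case against.** **The size rests on assumed responses.** This stands. Nothing in the documents says where the ratings will fall. A reader might expect satisfaction ratings to cluster at agree and infer one large loss. The documents do not support that: a self-directed control arm asked whether its sleep improved or whether it achieved real success need not answer near the top. With balanced answers the loss is 4-10%.

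**The formula is not the planned model.** This also stands. The SAP model has three arms and adjusts for sex and for weight change, which the intervention itself affects. The percentages are therefore indicative. The direction of the loss under proportional odds is not in doubt.

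**Three levels have some merit.** A reader might infer that the recode gains nothing for the model. That goes too far. Three levels need proportional odds over two cut-points rather than four, and they avoid thin end categories: at 55 per arm, a 3-5% category holds about two or three people (55 × .03 = 1.7; 55 × .05 = 2.8). The agree/neutral/disagree summary is also easy to read. The SAP invokes none of this, and a display table provides the readability without being the basis for testing.

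**Little depends on these tests.** Protocol Section 4 says only that satisfaction and well-being will be assessed at the end of the study. It does not make the between-program comparison a stated objective. Twenty items with two comparisons each give 40 unadjusted tests per analysis population. This limits the importance of the point but does not justify the less precise coding.

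**The recode is open.** It is specified in SAP 8.2 and in a table title, so it can be read as added detail to a general protocol sentence. It is fair not to call it concealed or data-driven. Even so, SAP 9.0 does not name the coding and no reason is given.

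**Conclusion.** The point holds as a low-severity improvement. The between-group tests use three levels where the planned model would take the five collected, and this lowers their precision.

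The loss cannot be stated as one figure. Near the null, under proportional odds and without covariates, it is about 4-13% for balanced or mildly agree-leaning responses, about 20-35% for clearly agree-leaning ones, and above 50% with a strong ceiling in which the two agree levels are both well filled.

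A reader might also infer that data are thrown away. They are not: Table 4.8.1 reports all five levels by arm, so the loss concerns inference only. The primary analysis and the sample size are unaffected.

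**What to change.** 1. State in SAP 9.0 that the cumulative logit model for these items is fitted to the five levels as collected.
2. Add the intervention and group-comparison p-values to Table 4.8.1.
3. Keep the three-level recode in Table 4.8.2 as display or as a sensitivity analysis.
4. If the recode is kept for testing, give the reason and list it in Section 14.

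The cost is SAP wording and an edit to the shells; the model is the same. The statistical price is proportional odds assumed over four cut-points instead of two, with sparser end categories. The three-level analysis can serve as the check on that.
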